8.1. Data Collection

Data generated will be collected by SCTRU, who will be responsible for checking the data, entering it on the trial database and validating it. The data collected will include:

- initial clinical details at enrolment
- outcome of surgical procedure
- outcome of histopathology evaluation of surgical specimens
- PSMA PET/CT report

8.2. Record Keeping and Archiving

SCTRU will store study documentation until the end of patient follow up. The documentation will then be archived according to current legislative requirements.

9. STATISTICS

9.1. Sample Size

If we identify 60 eligible patients we will formally analyse the relationship between PSMA expression in primary tumour and the incidence of pelvic nodal disease.

9.2. Randomisation and Stratification

No randomisation will be performed as this is a single arm study.

9.3. Analysis Plan

A binary logistic regression model will be trained on the SUV values obtained from the PSMA PET/CT imaging to predict whether metastatic disease is present or not. The analysis will be carried out on a (i) per-patient, (ii) bilateral side, (iii) LN-region, and (iv) LN-specific basis (as previously described by Leeuwen et al [9]). Where necessary, a generalized estimating equation model will be used to adjust for correlations within regions of each patient. Performance on unseen data will be assessed using 10-fold cross validation, and calculating sensitivity, specificity, positive predictive value (PPV) and negative predictive value (NPV). The "gold standard" assessments to which the model predictions will be compared will be provided by pathology.

Comparison of PSMA PET/CT reporting between local nuclear physician evaluation and review by central experts will be represented in a Bland Altman plot. A consensus will be developed in terms of minimum training required for local nuclear physicians in the review of PSMA PET signals.

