Images from ⁶⁸Ga-PSMA PET/CT scanning will be interpreted by two experienced nuclear medicine physicians (one at the local scanning site as well as central reporting by an expert nominated from the PSMA imaging subgroup). All LNs with increased ⁶⁸Ga-PSMA accumulation will be assigned to their respective anatomical location, measured in the short axis, along with an assigned SUVmax for each affected LN. In addition, visual analysis of the ⁶⁸Ga-PSMA uptake will included a four-point certainty scoring scale (definitely negative, equivocal probably negative, equivocal probably positive, definitely positive). Although not our primary research focus, PSMA +ve lesions within the prostate will be categorised as either focal or diffuse. Disease involving only one of the four prostatic quadrants will be considered as focal. If prostatic lesions are detected in more than one quadrant, the disease will be classified as diffuse/multifocal (if non-contiguous). Signals that indicate potential distant metastatic sites will also be scored using the four-point certainty scoring scale as described above for pelvic nodes [13].

Attention will be paid to ensure comparable imaging protocols are used across participating sites to ensure data obtained are suitable for objective and robust reporting of PSMA PET/CT across the study. Lesion uptake will be categorised according to a predefined anatomical scoring template.

Image scoring

Interpretation of PET imaging will be performed in accordance with the NCRI PET framework. All positive LNs on ⁶⁸Ga-PSMA PET/CT will be assigned to the respective anatomical region: left/right external iliac; left/right internal iliac, left/right obturator; left/right fossa of Marcille. Positive matching will be defined as the correlation between PET scan positivity and histological positivity, with histopathological analysis of the LNs considered the reference standard. Positive nodes in each nodal region/chain will be scored individually. These data can then be analysed separately or collectively for each nodal region. Once recruiting sites have satisfied QC evaluation by the UK PET Core Lab, the SUV values will be generated by identical (or very similar) reconstruction algorithms and are expected to be reproducible across the study.

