3.5. Endpoints

Primary Outcomes:

- 1. To establish whether prostate tumours with high PSMA expression have enhanced risk of pelvic nodal metastasis.
- 2. To establish best practice and optimise protocols for multi-centre application of PSMA PET/CT imaging.

Secondary Outcomes:

- 1. To evaluate the feasibility of a future large scale randomised controlled trial (RCT), and develop quality assurance measures across the study team/network.
- 2. To develop a platform to carry out RCT to study the usefulness of novel imaging/biomarkers for evidence-based treatment decisions in patients at risk of pelvic nodal prostate cancer.

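### Section 9.3 never ties its SUV model to primary-tumour PSMA, the predictor of primary outcome 1, and its side, region and node levels fit nodal staging instead

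*Protocol*

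**What the plan says.** Section 3.5 (and section 2) gives primary outcome 1 as: "To establish whether prostate tumours with high PSMA expression have enhanced risk of pelvic nodal metastasis". Section 9.1 adds that, with 60 eligible patients, "we will formally analyse the relationship between PSMA expression in primary tumour and the incidence of pelvic nodal disease". In both places PSMA is measured in the primary tumour and the outcome is nodal disease.

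Section 9.3 holds the only model in the protocol: "A binary logistic regression model will be trained on the SUV values obtained from the PSMA PET/CT imaging". It does not say which lesion's SUV is meant. The levels follow: "The analysis will be carried out on a (i) per-patient, (ii) bilateral side, (iii) LN-region, and (iv) LN-specific basis". For these it refers to a published study that the reference list describes as one of preoperative lymph node staging. For clustering, where needed, "a generalized estimating equation model will be used to adjust for correlations within regions of each patient". Performance is cross-validated sensitivity, specificity, PPV and NPV against pathology, with no cut-off stated.

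Section 3.1 describes what is measured. SUVmax is taken for lesions, chiefly pelvic nodes, with prostate signals also assessed. Each node with raised uptake gets its own SUVmax and is placed in one of eight regions (four per side). Prostate lesions are classed by extent: "Disease involving only one of the four prostatic quadrants will be considered as focal". The protocol does not say how several prostate lesions become one value per man.

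**The concern.** Two different questions pass through one model statement. The first is whether men whose primary tumour expresses more PSMA are more likely to have nodal metastasis. That compares men. The second is whether uptake in a node, region or side shows that this unit contains cancer. That is staging accuracy, and it is where sub-patient levels make sense.

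Because section 9.3 does not name the SUV, an analyst can follow it to the letter and report nodal-SUV accuracy as the primary result, leaving outcome 1 unanswered. An analyst can equally carry the tumour's SUV down to regions and nodes, where it cannot tell a diseased unit from a healthy one in the same man. A real association between men could then be reported as poor prediction.

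**Working it through.** **1. The two readings side by side**

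| | Nodal SUV | Primary-tumour SUV |
|---|---|---|
| Support in the text | Section 3.1: SUVmax per affected node, placed by region; section 9.3: levels borrowed from a nodal-staging study | Sections 2, 3.5 and 9.1: outcome 1 |
| Per-patient level | Not the predictor of outcome 1 | Answers outcome 1 |
| Region and node levels | Sensible as staging accuracy | Same prediction for every region and node of a man |

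Neither reading makes all four levels an analysis of outcome 1. The GEE does not change this: it allows for within-man correlation but creates no within-man contrast in a covariate that has none.

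**2. Inputs for the size of the effect under the tumour reading**

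From the cohort cited in section 1.3: 30 men, 12 node-positive, 608 nodes, 53 metastatic. PET was true positive in 4 men and false negative in 8.

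Reproducing the stated patient-level accuracy with TP 4, FN 8, FP 0, TN 18:
- sensitivity 4/12 = 33.3%
- specificity 18/18 = 100%
- PPV 4/4 = 100%
- NPV 18/26 = 69.2%

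All four agree with section 1.3.

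**3. A perfect between-man predictor, scored on nodes**

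Suppose the tumour score separates the 12 positive from the 18 negative men without error, so that patient-level accuracy is 100% on every measure. Call every node of a positive man positive. Let r be the mean node yield of positive men divided by that of negative men. The protocol does not give r, so it is an assumption.

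- Nodes called positive: C = 608 × 12r/(18 + 12r)
- PPV = 53/C
- Specificity = (608 − C)/(608 − 53)

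| r | C | PPV | Specificity |
|---|---|---|---|
| 0.5 | 152.0 | 34.9% | 82.2% |
| 1 | 243.2 | 21.8% | 65.7% |
| 2 | 347.4 | 15.3% | 47.0% |

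**4. Region level**

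There are eight regions per man. Assume k of 8 are positive in each node-positive man. Then PPV = k/8 and specificity = (18 × 8)/(240 − 12k). For k = 1 to 4, PPV runs from 12.5% to 50% and specificity from 144/228 = 63% to 144/192 = 75%.

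**5. Dependence on the cut-off**

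At r = 1 the fitted probability for a node in a positive man is 53/243.2 = 0.218. With a cut-off of 0.5, no node is called positive: sensitivity 0%, specificity 100%, PPV undefined. Without any cut-off, the AUC of this two-valued score is 0.657 + 0.5 × (190.2/555) = 0.83, although it separates the men perfectly.

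**6. Are these upper limits?**

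No. Assume the 53 metastases fall over the 12 men as 1, 1, 1, 1, 2, 2, 3, 4, 6, 8, 10, 14, with equal node yield (608/30 = 20.27 per man) and a score that rises with nodal burden. Calling positive only the six men with at least three metastatic nodes selects 121.6 nodes, of which 45 are metastatic:
- PPV 45/121.6 = 37%
- sensitivity 45/53 = 85%
- specificity (555 − 76.6)/555 = 86%

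The node-level AUC of that score is 0.93.

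**The case against.** The strongest reply is that the protocol nowhere puts tumour SUV into a node-level model. Section 3.1 gives nodes their own SUVmax, scores positive nodes by region and matches PET to histology. Section 1.4 describes a staging test. On that reading the figures in steps 3 to 5 do not apply. This stands, and it is why they are offered only as an illustration. It does not rescue the plan, because a nodal-SUV model does not address outcome 1.

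A second reply is that the per-patient level is listed first and section 9.1 counts patients, so outcome 1 already has its level. The level is there, but the predictor is not: even the per-patient model is not tied to the primary tumour.

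A third is that naming a covariate for each level belongs in a statistical analysis plan, which is not at hand, and that the cited staging study may settle it. Detail can indeed be left to such a plan. Here, however, the protocol has already fixed one model at four levels, and that does not match its own primary outcome.

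A reader might also infer that 22% and 66% are built-in limits for any tumour marker. They are not: they depend on node yield, the cut-off and the borrowed cohort, and a score that tracks nodal burden can exceed them (step 6). Nor does the protocol state that each man has a single tumour value, since prostate disease may involve several quadrants. That might suggest a side-level comparison using each half of the prostate. But section 3.1 uses quadrants only to class disease as focal or diffuse and does not say that SUVmax is recorded by half. Conditioning within man on raw SUVmax would also not remove multiplicative scale differences between scans.

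**Conclusion.** The concern holds in this form: the one model in section 9.3 is not tied to the predictor of primary outcome 1, and no single choice of SUV makes its four levels answer that outcome. With nodal SUV, the likelier reading below patient level, the result is staging accuracy. With tumour SUV, region- and node-level accuracy cannot discriminate within a man and would understate how well the marker separates men.

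In the cited cohort, a predictor that is perfect between men would show node-level PPV of about 22% and specificity of about 66%, or 15-35% and 47-82% for relative node yields of 2 to 0.5. These figures assume that the cohort's prevalence at patient level (40%) and node level (53/608 = 8.7%) carries over, and that all nodes of positive men are called positive. They show the direction and possible size of the distortion, not a limit. The mismatch between outcome and model does not depend on them.

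**What to change.** Split section 9.3 into two named analyses.

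(a) Primary outcome 1: a per-patient logistic model of pelvic nodal metastasis (present or absent on pathology) on primary-tumour SUVmax, named as the analysis of that outcome. State how several prostate lesions reduce to one value per man.

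(b) Nodal staging accuracy: side-, region- and node-level analyses using the nodal SUV of that unit, with the GEE for clustering, labelled as such. Because section 3.1 assigns SUVmax only to nodes with raised uptake, state what value a unit without uptake takes.

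Do not report region- or node-level sensitivity, specificity, PPV or NPV for primary-tumour SUV.

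The cost is wording in the protocol or the statistical analysis plan. No further patients, scans or visits are needed, since section 3.1 already has prostate signals assessed alongside nodal ones.

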3. TRIAL DESIGN

3.1. General Design

[figure not shown]
We propose to carry out a PSMA expression feasibility study in a cohort of patients with high risk prostate cancer (in the absence of clinical evidence for distant metastasis) opting for surgical intervention with radical prostatectomy (RP) and extended pelvic lymphadenectomy (ePLND). Sixty patients will be recruited from 4 centres within the United Kingdom, namely Addenbrookes Hospital, Cambridge; Queen Elizabeth University Hospital, Glasgow, University College London Hospital, London and St Bartholomew's Hospital, Barts Health NHS Trust, London. The study will include patients with NCCN (National Comprehensive Cancer Network) high-risk prostate cancer (as defined by one or more of the following: PSA \geq 20ug/L, Gleason sum score \geq 8, T-stage \geq cT3).

Patients with high risk prostate cancer being considered for radical prostatectomy and pelvic node dissection will have a PSMA PET/CT scan as part of standard of care imaging. Standard of care imaging will be as per local clinical practice (MRI/CT/bone scintigraphy/non-PSMA PET scans), with PSMA PET scan performed in lieu of isotopic bone scan.

Patients who have given signed or verbal informed consent and who have met all eligibility criteria will be enrolled into the trial.

Patients will be recruited from the participating centres within a 6 month period. These patients with high-risk disease will be managed as outlined in Figure 1.

Figure 1. Study outline

Template based extended pelvic lymph node dissection and approach for pathological evaluation of specimens

For patients recruited to this study, an ePLND will be performed at the time of RP, removing lymphatic tissue up to the bifurcation of the common iliac artery, along the external iliac (with the distal limit at the deep circumflex vein and femoral canal), the internal iliac vessels and the obturator fossa, as well as the fossa of Marcille. The lateral limit of the template is at the external iliac vein and the medial limit is the perivesical fat [1, 10]. All specimens will be submitted by the surgeon in separate formalin–filled containers, labelled according to their anatomical location, i.e. left/ right external iliac, left/ right internal iliac, left/ right obturator and left/right fossa of Marcille.

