After dissection, specimens from all enrolled patients will be sent for histopathological examination in line with the International Society of Urological Pathology (ISUP) consensus conference [11] and the UK Royal College of Pathologists (RCPath) dataset [12] by designated uropathologists at the study sites. RP specimens will be processed according to routine clinical protocol of the study sites. Lymphatic tissue will be examined by palpation, visual inspection and sectioning at 3 mm intervals, in accordance with a consensus protocol within this study. The transversely sliced lymph nodes (LNs) will be processed, paraffin-embedded and histological sections cut and stained for Haematoxylin and Eosin (H&E). Disease positivity will be defined as the presence of any metastatic deposits of prostate cancer in the LNs examined. For each metastatic LN, both the short axis and largest diameter (expressed in mm) of the metastatic deposits will be recorded. The number of positive nodes and the total number of nodes found will be reported for each of the nodal specimens submitted.

PSMA PET imaging and reporting

Lesions detected by PSMA imaging will be evaluated by their maximum Standardised Uptake Values (SUVmax), which provides an objective quantification of each abnormal lesion, with particular interest for the pelvic lymph nodes, but signals in the prostate, bone and other soft tissue if present will also be assessed. There is a small chance of potential occult distant metastasis being identified in PSMA PET/CT imaging. Regardless of the results of the PSMA PET imaging, ePLND will include clinically recommended anatomical template. Following surgery, the need for additional investigation to clarify the validity of PSMA PET/CT revealed signals will be at the discretion of the clinical team and will not be dictated by the trial. For instance, increased uptake in solid organs or bone may result from Paget's disease or haemangioma, which may require additional correlative imaging.

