5.2.2 Surgery - Radical Prostatectomy and Pelvic Node Dissection

Pathology

Surgical specimens from radical prostatectomy (RP) and pelvic node dissection will be processed at each of the participating centres for histopathological examination in line with the International Society of Urological Pathology (ISUP) consensus conference [11] and the UK Royal College of Pathologists (RCPath) dataset [12] by designated uropathologists.

Lymphatic tissue will be examined by palpation, visual inspection and sectioning at 3 mm intervals, in accordance with a consensus protocol within this study. The transversely sliced lymph nodes (LNs) will be processed, paraffin-embedded and histological sections cut and stained for Haematoxylin and Eosin (H&E). Disease positivity will be defined as the presence of any metastatic deposits of prostate cancer in the LNs examined. For each metastatic LN, both the short axis and largest diameter (expressed in mm) of the metastatic deposits will be

recorded. The number of positive nodes and the total number of nodes found will be reported for each of the nodal specimens submitted.

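### Node-level accuracy cannot be determined in regions with mixed PET and histology results, because region is the only link between them; pelvic nodes outside the eight regions have no class

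*Protocol*

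**What the plan says.** Section 9.3 states the model and the levels of analysis. "A binary logistic regression model will be trained on the SUV values obtained from the PSMA PET/CT imaging to predict whether metastatic disease is present", and the analysis is to run on a "i) per-patient, (ii) bilateral side, (iii) LN-region, and (iv) LN-specific basis". Sensitivity, specificity, PPV and NPV are to be calculated, with pathology as the reference. For the four levels the section refers to a published study and does not reproduce its method.

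The data for the fourth level are described in sections 3.1 and 5.2.2:

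- **Surgery (3.1).** "All specimens will be submitted by the surgeon in separate formalin–filled containers, labelled according to their anatomical location". The locations are external iliac, internal iliac, obturator and fossa of Marcille, left and right: eight regions.
- **Pathology (3.1 and 5.2.2).** "The number of positive nodes and the total number of nodes found will be reported for each of the nodal specimens submitted". In addition, "For each metastatic LN, both the short axis and largest diameter (expressed in mm) of the metastatic deposits will be recorded".
- **PET (3.1, imaging and reporting, and image scoring).** Each node with increased uptake gets a location, a short-axis measurement and an SUVmax. "Positive nodes in each nodal region/chain will be scored individually". All PET-positive nodes are assigned to the same eight regions. Possible distant sites are scored separately for certainty.
- **Matching (3.1, image scoring).** A positive match is defined as PET positivity correlating with histological positivity. The unit of matching is not given.

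**The concern.** An LN-specific accuracy table needs to know which excised node is which PET node. The planned records share one key, the region. Size cannot serve as a second key, because PET measures the node and histology measures the metastatic deposit. Nodes without increased uptake also have no stated SUV, so the model in 9.3 has no stated predictor value for them at this level.

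If a container holds several nodes, some metastatic and some PET-positive, the analyst must assume which belong together. Assuming the best match favours the scan, and nothing in the results would show it. Section 1.3 names the size threshold for detection as an open need, and that question depends on the same link.

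There is a second gap in the region list. A pelvic PET-positive node outside the eight regions is also outside the dissection template, so it has no planned histology, and the rule for all positive nodes offers no class for it. Placed in a histology-negative region it would count as an unverified false positive. Placed in a histology-positive region that PET otherwise missed, it would turn a false negative into an unverified true positive.

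**Working it through.** The protocol gives no figure for this point, so there is none of its own to reproduce. The check asks what the planned records determine.

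**1. Bounds within one container.** Let T be the nodes found, H the metastatic nodes and P the PET-positive nodes. Assume every PET-positive node assigned to the region is among the T nodes retrieved. The node-level true positives then satisfy

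max(0, H + P − T) ≤ TP ≤ min(H, P).

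The remaining cells follow: FN = H − TP, FP = P − TP, TN = T − H − P + TP.

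**2. When the bounds meet.** They coincide if H = 0, P = 0, H = T or P = T. Otherwise the container is mixed on both tests and TP is not determined.

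| T | H | P | TP | Sensitivity | Specificity |
|---|---|---|---|---|---|
| 3 | 1 | 0 | 0 | 0% | 100% |
| 3 | 1 | 1 | 0 or 1 | 0% or 100% | 50% or 100% |
| 3 | 2 | 2 | 1 or 2 | 50% or 100% | 0% or 100% |
| 3 | 1 | 3 | 1 | 100% | 0% |

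In the second row PPV is also 0/1 = 0% or 1/1 = 100%.

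**3. Where the true positives lie.** TP > 0 requires H > 0 and P > 0. Such containers are determined only if H = T or P = T. The numerator of sensitivity and PPV therefore comes from the part of the data that is otherwise ambiguous.

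**4. Nodes per container.** The surgical series in section 1.3 had 608 nodes in 30 patients: 608/30 = 20.3 per patient, and 20.3/8 = 2.5 per region if spread over eight regions. Containers with more than one node should be common.

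**5. Patients who could be affected.** The same series had 12 node-positive patients, of whom 4 were true positive and 8 false negative on PET. With specificity 100% the other 18 were PET-negative. This reproduces its reported sensitivity (4/12 = 33.3%) and NPV (18/26 = 69.2%). So 26 of 30 patients had no PET-positive node and are fully determined.

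- At that rate, at most 60 × 4/30 = 8 of 60 patients could have an ambiguous container.
- At the upper end of the sensitivity range quoted in 1.3 (85%), treated as per-patient, and with 40% node-positive (12/30), the limit is 60 × 0.40 × 0.85 = 20.4, about 20 of 60.

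Patients with PET-positive nodes but no metastasis do not add to these limits, because H = 0 determines their tables.

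**The case against.** A reader might infer that the whole node-level analysis would be invented. Scaling the cited series to 60 patients gives 608/30 × 60 = 1,216 nodes and 53/30 × 60 = 106 metastases, and all of these might seem to be without a verifiable link. The documents do not support that. Total and positive counts are reported per container, so most containers are likely to be determined without any matching, and pathology does record deposit size for each metastatic node. This part of the objection stands and limits the problem to containers mixed on both tests.

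Nor does the protocol say that a PET-positive node counts as a true positive whenever any node in its region is metastatic. An upward bias is the result of one possible rule, not of a stated one. The cited study, the pathology consensus protocol mentioned in 3.1 or an SAP may contain a matching rule; none can be checked here. But a rule written at analysis cannot recover a link that was not recorded at surgery, pathology and reading.

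It is also too broad to say that uptake outside the regions has no category. Possible distant sites are scored, and 3.1 mentions a predefined anatomical scoring template. The gap is confined to pelvic nodes outside the eight listed regions, and the direction of the resulting error is not fixed.

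Finally, this is one of four levels in a feasibility study whose primary outcome concerns PSMA expression in the primary tumour. That is correct and limits the weight of the point. It does not make the planned node-level sensitivity and PPV estimable.

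**Conclusion.** The point holds in limited form. Section 9.3 commits to LN-specific accuracy, but the records described in 3.1 and 5.2.2 do not identify node-level true positives in containers mixed on both tests. Sensitivity and PPV carry most of the uncertainty, because their numerator comes only from containers positive on both tests.

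The number of patients affected is at most about 8 of 60 at the cited series' detection rate, and about 20 of 60 at 85% sensitivity. Both figures assume that series' 40% prevalence and 100% patient-level specificity carry over; the second also treats the quoted 85% as per-patient. They are upper limits, since not every PET-positive, node-positive patient will have a mixed container.

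The missing class for pelvic nodes outside the template is a separate, smaller gap. The documents give no figure from which to size it.

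The per-patient, side and region analyses and the primary outcome are not affected by the node-matching problem. Miscoded nodes from outside the template could still affect accuracy at those three levels. The change should be made before specimens and reads accumulate.

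**What to change.** 1. In 9.3, make LN-region the finest level for point estimates of accuracy: any metastasis in the container against the PET call for that region.
2. Report any LN-specific result only as lower and upper bounds summed from the container counts. Alternatively, give point estimates in fully determined containers only, labelled as such. The second option is selective. With T = 3 and H = 1 it keeps every missed container (P = 0) and drops those with P = 1 or 2, so its sensitivity should not be read as that of the whole cohort.
3. For the size question, relate the largest metastatic deposit in each region to that region's PET call, across all histology-positive regions including those PET missed entirely. Restricting to regions with one PET-positive and one metastatic node would still assume the link and would exclude the misses.
4. Add a read-form code, *outside template – not verified*. Exclude such lesions from region-level accuracy, and show per-patient results with and without them.

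The cost is protocol or SAP wording and one extra code on the read form, with no added procedure for patients. The downside is that there will be no single node-level figure to set beside the cited study.

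### Section 9.3 names only a Bland-Altman plot for local-versus-central reads; this does not fit the categorical calls and leaves out nodes marked by one reader alone

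*Protocol*

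**What the plan says.** Section 9.3 (Analysis Plan) gives the reader comparison one sentence: "Comparison of PSMA PET/CT reporting between local nuclear physician evaluation and review by central experts will be represented in a Bland Altman plot". It names no plotted quantity, no second measure of agreement and no threshold for acceptable agreement. The next sentence announces a consensus on the minimum training that local readers need.

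Section 3.1 sets out what is compared. Scans "will be interpreted by two experienced nuclear medicine physicians (one at the local scanning site as well as central reporting by an expert". The reads yield:

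- a visual score on "a four-point certainty scoring scale (definitely negative, equivocal probably negative, equivocal probably positive, definitely positive", which is ordinal;
- a region for each positive node, "left/right external iliac; left/right internal iliac, left/right obturator; left/right fossa of Marcille", which is nominal with eight levels;
- for nodes with raised uptake, a size and an uptake value: they are "measured in the short axis, along with an assigned SUVmax for each affected LN". These are continuous but exist only for nodes that a reader marked;
- a two-way class for the primary: "PSMA +ve lesions within the prostate will be categorised as either focal or diffuse".

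The same section says that lesions "will be evaluated by their maximum Standardised Uptake Values (SUVmax), which provides an objective quantification of each abnormal lesion". Section 3.5 lists best practice for multi-centre PSMA PET/CT as the second primary outcome.

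**The concern.** A Bland-Altman plot is made for paired measurements on a continuous scale. It shows each pair's difference, the mean difference, and limits at the mean plus or minus 1.96 SD. Only SUVmax and short axis are of that kind here. Whether a node is called, how certain the reader is and where the node is placed are categorical.

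This creates two gaps. If the score is plotted, differences can only be whole numbers from -3 to 3, over-calls and under-calls offset each other in the mean, and the limits need not stay within the scale. If SUVmax or short axis is plotted, a node marked by one reader has no partner and disappears. Such nodes are the missed or extra calls that reader training would address. Either way, the one stated method leaves agreement on detection without a proper measure, although that agreement bears on the second primary outcome.

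**Working it through.** The protocol gives no figure for reader agreement, so there is none to reproduce. The check is a constructed example.

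**Inputs.** 60 patients (Section 3.1) and eight nodal regions (Section 3.1, Image scoring) give 60 x 8 = 480 patient-regions. Scores are coded 1 to 4. A region in which a reader marks nothing is taken as definitely negative; this is an assumption. The number m of definitely positive regions per reader is also assumed (8 to 48), because the protocol states no expected PET-positive rate for this study. For context, the 30-patient cohort described in Section 1.3 had 4 true positives and 100% specificity, so 4 of 30 patients were PET-positive; carried over, that is 8 patients in 60. No positive region is shared between readers, which is the extreme case.

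**Region level.** The differences are +3 (m times), -3 (m times) and 0 otherwise.

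- Mean difference = (3m - 3m)/480 = 0.
- SD = sqrt(18m/479); limits = ±1.96 SD.
- With p = m/480: raw agreement = 1 - 2p; chance agreement = p² + (1 - p)²; kappa = -p/(1 - p). Quadratic-weighted kappa is the same here because only the two end categories occur.
- Positive agreement = 2a/(2a + b + c) with a = 0, so 0%.

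| m per reader | Mean difference | Limits (points) | Raw agreement | Kappa | Positive agreement |
|---|---|---|---|---|---|
| 8 | 0 | ±1.07 | 97% | -0.02 | 0% |
| 12 | 0 | ±1.32 | 95% | -0.03 | 0% |
| 24 | 0 | ±1.86 | 90% | -0.05 | 0% |
| 48 | 0 | ±2.63 | 80% | -0.11 | 0% |

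Raw agreement stays at 80% or more, so percentage agreement alone would not be an adequate replacement.

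**Patient level, readers calling different patients positive.** With n patients positive per reader out of 60 and none shared, SD = sqrt(18n/59). For n = 12, SD = 1.91 and the limits are ±3.75. For n = 24, SD = 2.71 and the limits are ±5.30. The largest possible difference is 3, so these limits describe values that cannot occur.

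**Patient level, same patients but different regions.** If each patient is summarised by the highest score or the number of positive regions (at most one per reader), every difference is 0, so the mean and the limits are both 0. Kappa on that summary would also show perfect agreement. This case therefore shows that a per-region analysis is needed; it does not separate the two methods.

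**SUVmax or short axis.** With no node marked by both readers there are no pairs, so there is nothing to plot.

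**The case against.** The strongest reply is that the sentence may be meant for SUVmax. Uptake values are the only PET variable named elsewhere in Section 9.3, Section 3.1 calls SUVmax an objective quantification and expects SUV values to be reproducible once sites pass quality control, and Bland-Altman is a standard choice for that. This stands as a possible reading. But the sentence speaks of reporting in general, and on the SUVmax reading nodes marked by one reader still fall out.

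A reader might infer that the read is purely ordinal and that the method is therefore wrong altogether. Section 3.1 does not support this, since two of the outputs are continuous.

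A reader might also infer that the plot would hide total disagreement, or could not show over- or under-calling. That goes too far. In the region-level example every discordant region sits at +3 or -3, outside the limits; overprinting would hide how many there are, not that they exist. Systematic over-calling moves the mean: 24 extra local calls with none in return give 24 x 3/480 = 0.15 points. Only balanced errors cancel.

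Finally, the choice of agreement statistics is often left to the SAP, which was not available, and naming one display excludes no other. That is fair for details such as kappa weights. Here, however, the protocol does fix a method, and that method covers only part of what it is meant to compare.

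**Conclusion.** The point holds in a limited form. Bland-Altman is adequate for SUVmax and short axis of nodes marked by both readers. It does not fit the certainty score, the region or the focal/diffuse class, and it leaves out nodes marked by one reader. Section 9.3 names nothing else and does not say what is plotted.

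The figures show what can happen, not what is expected. They rest on an assumed 8 to 48 positive regions per reader, on none being shared, and on unmarked regions counting as negative. Real readers will share some positives.

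It would be too strong to say that the training consensus or the second primary outcome depends on this plot. Section 9.3 places the consensus next to it without a decision rule, and Section 5.2.1 also provides Core Lab accreditation, review of local protocols and technical checks of scans. The analysis of primary-tumour PSMA expression against nodal disease is not affected. The change is worth making, but the matter is one of analysis wording.

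**What to change.** In Section 9.3, or in the SAP with a reference from Section 9.3:

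- State which outputs are compared. Restrict Bland-Altman to SUVmax and short axis of nodes marked by both readers. Use the log scale only if the differences are seen to grow with magnitude; the protocol gives no ground for assuming this beforehand.
- For the four-point score, report the 4x4 cross-table and weighted kappa. Report positive and negative specific agreement (the two positive categories against the two negative ones) per region and per patient. Give 95% confidence intervals that allow for clustering within patient, for example from a patient-level bootstrap.
- Tabulate the focal/diffuse class the same way, as a 2x2 table.
- Give the number of nodes marked by the local reader only, by the central reader only, and by both.
- State how a region with no marked node is scored, so that the tables have a defined denominator.

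The reads already planned supply the data, provided that unmarked regions are given a defined score. The cost is a change of wording and slightly more analysis. The drawback is that reported agreement may look less favourable, and kappa in particular will be sensitive to few positives, which is why specific agreement should stand beside it.
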